2.2.2 SECONDARY ENDPOINTS

a) Efficacy as measured by Clinical Benefit Rate (percentage of patients with stable disease or better using MRI/CT imaging) at 6 and 12 months after intervention commencement. Stable disease is defined as MRT/ATRT/Osteosarcoma with complete response (CR), partial response (PR), minor response (MR), stable disease (SD) overall response. Neuroblastoma with CR/PR/SD or Non-CR/Non-PD overall response.

2.2.3 EXPLORATORY ENDPOINTS

a) Comparing overall and event free survival for ATRT patients to historical data. Comparison of EFS and OS up to 2 years post enrolment.

2.3 STUDY POPULATION

Inclusion criteria:

- Patients must be < 40 years of age.
- Patients with refractory or relapsed osteosarcoma, neuroblastoma and MRT/ATRT or newly diagnosed MRT/ATRT. Patients must have had histological verification of the diagnosis of malignancy at time of diagnosis or relapse.
- Patient's disease is considered refractory, according to their treating hospital standard practice guidelines, to conventional therapy except for newly diagnosed ATRT/MRT. This includes relapsed patients who may be off treatment. Patients must have stable disease (SD) or better.
- Karnofsky $\geq 60\%$ for patients ≥ 16 years of age, OR Lansky $\geq 60\%$ for patients < 16 years of age.
- Life expectancy of greater than 8 weeks.
- Fully recovered from acute toxic effects of all prior chemotherapy, immunotherapy or radiotherapy prior to entering study.
- Patients with CNS tumours who are receiving dexamethasone must be on a stable or decreasing dose for at least 1 week.
- Adequate BM function – peripheral ANC $\geq 750/\mu\text{l}$ ($0.75 \times 10^9/\text{L}$); platelet count $\geq 75,000/\mu\text{l}$ ($75 \times 10^9/\text{L}$); haemoglobin $\geq 8\text{g/dL}$ (80 g/L).
- Adequate renal function – age-adjusted normal serum creatinine or GFR $> 70\text{ml/min}/1.73\text{m}^2$.
- Adequate liver function – total bilirubin $\leq 1.5 \times \text{IULN}$ for age, ALT $\leq 5 \times \text{IULN}$ for age, and albumin $\geq 2\text{g/dL}$ (20g/L).
- Adequate cardiac function – shortening fraction of $\geq 27\%$ OR ejection fraction of $\geq 50\%$ by echocardiogram.
- Adequate respiratory function defined as no evidence of dyspnoea at rest, no exercise intolerance and pulse oximetry (SaO_2) $> 94\%$ in room air.
- Adequate CNS function – seizure free for 2 months.

- Adequate serum calcium, magnesium, and potassium concentrations – all must be \geq ILLN for age, with or without supplementation.
- If female and post-menarcheal, pregnancy test must be negative.
- If of reproductive potential, have agreed to use effective contraceptive method.
- If female and lactating, have agreed not to breastfeed.
- Patient and/or their legal representative have signed a written informed consent form.

Exclusion criteria:

- Patients who have received myelosuppressive chemotherapy and/or biologic therapy within 3 weeks (4 weeks if prior nitrosourea).
- Patient has received local palliative radiotherapy within 2 weeks.
- Patient has received craniospinal radiotherapy within 3 weeks.
- Patient has received \geq 50% radiation of pelvis within 6 weeks.
- Patient has received other substantial BM radiation within 6 weeks.
- Have received growth factor(s) within 1 week.
- Are receiving enzyme inducing anticonvulsant therapy. In order to be eligible, patients must be transferred to and stabilised on an eligible anticonvulsant as listed in Appendix II as per local institutional practice. (See Appendix II for a list of enzyme inducing and nonenzyme inducing anticonvulsants).
- Are on medications associated with prolongation of QTc interval as listed in Appendix III.
- Are receiving hydrochlorothiazide.
- Are receiving metronidazole and/or disulfiram. This is due to the increased risk of metabolic acidosis when patients are concomitantly on panobinostat and metronidazole and/or disulfiram.
- Patients with uncontrolled sepsis.
- Patients who have previously received panobinostat.
- Patients with symptoms of congestive heart failure, uncontrolled cardiac rhythm disturbance, or a QTc (Fridericia's formula) that is > 450 msec.

2.4 INTERVENTION

A three-week washout period was required after conventional myelosuppressive chemotherapy and/or biologic therapy to start Panobinostat therapy.

Panobinostat was supplied in capsule form and administered orally. Each course consisted of 4 weeks (28 days). Treatment will continue for up to 12 months consisting of 12 treatment courses, each of 4 weeks (28 days) duration.

Intra-patient dose adjustments of 2 mg/m² were made to a starting dose of 10 mg/m² based on DLTs/AEs and biological activity, and dose level for that stratum reviewed. For full criteria for dose escalation and reduction see protocol version 5.0 18Sep2020. The final dose per strata was the level where continuous dosing is maintained for a 4-week period with acceptable toxicity and biological effect.

Protocol therapy could be terminated for the following reasons: a)
Progressive disease (radiographic or clinical)

- b) Irreversible or unacceptable dose-limiting toxicity
- c) Other adverse event
- d) Refusal of further protocol therapy by patient or parent/guardian
- e) Physician determines it is not in the patient's best interest
- f) Pregnancy
- g) Termination or suspension of clinical trial

The investigator's clinical judgment was used to determine whether a subject should be removed from treatment or from the study due to progressive disease, AE or DLT, or another reason.

2.5 RANDOMISATION AND BLINDING

This a single arm open label study.

2.6 SAMPLE SIZE

The study employed a Simon two-stage minimax design (1). A 30% gain in Clinical Benefit Rate (CBR) was considered as the minimum gain required to warrant further study of this regimen. In this case the clinical benefit to be observed is stability of disease. 70% stability at 4 months would be indicative of clinical utility, whereas a rate of 40% would be the lower limit of interest, with $\alpha = .15$ and $\beta = .10$. The minimal accrual number required in each strata was 14 patients. This was increased to 20 patients in each strata, over 3 years, for a total of 60 patients.

The biological activity analysis was performed for a minimum of 2 patients in each strata at the required dose levels.

2.7 STUDY PROCEDURES

All entry requirements had to be completed during the four-week screening period before study enrolment.

Studies to be Obtained	Pre-salvage therapy ^a	Screening prior to enrolment (Baseline)	Weeks 1-4 (first 28 day course)	Subsequent Months (28 day courses)	Follow-up ^b
History (including AEs/DTs)		X	Weekly	X	X
Physical Exam (height, weight, BSA)		X	Weekly	X	X
Performance Status Refer to Appendix I		X	Weekly	X	X
Full Blood Evaluation (FBE) with Differential & Blood Film		X	Weekly	X	X
Urinalysis ^c		X	Weekly	X	
Urea & Electrolytes Calcium, Magnesium & Potassium		X	Weekly	X	X
Renal Function/GFR/Creatinine		X	Weekly	X	X
Liver Function Tests including Total Protein & Serum Albumin		X	Weekly	X	X

Thyroid Function Tests (TFTs including TSH, T3, T4)		X		End of therapy	
CT/MRI of Primary Tumour^d	X	X		2 monthly	X ^e
MRI Spine (ATRT only) Refer to Section Error! Reference source not found.	X	X		2 monthly ^f	X _{e,f}
FDG-PET/DOTATATE^g	X	X		2 monthly	X ^e
MIBG (Neuroblastoma only)		X	X	2 monthly	X ^e
CXR (ATRT only)	X	X ^h		End of therapy	
Abdominal Ultrasound (ATRT only)	X	X ^h		End of therapy	
MRI Brain (MRT only, not primary site)	X	X ^h		End of therapy	
CT Chest / CXR (Osteosarcoma only, non-lung primary)	X	X (CT and CXR)		2 monthly (CXR, CT and CXR at end of therapy)	X (CT or CXR)
Blood Samples – HDACi [Not applicable to United States]		Pretreatment	7 days after first dose		
Bone Marrow Evaluation (only if clinically indicated) including HDACi studies [Not applicable to United States]		X	End of Course	If positive at baseline or as clinically indicated	
Pregnancy Testⁱ		X			
ECG		X	End of Course	X	
Echocardiogram		X		6 monthly	

a If applicable and where available, these will be the last set of imaging investigations performed as part of routine patient care prior to salvage therapy.

b Up to 2 years from completion of therapy. c Not mandated at every time point, urinalysis performed per institutional practice.

d Use the same imaging modality throughout the course of the study e Follow-up imaging studies are not required if there is documented evidence of overt clinical progression. Follow-up imaging is 3 monthly or per routine follow-up.

f Repeat Spine MRI only if initially positive

g Use FDG-PET in non-CNS MRT.

Use FDG-PET in all osteosarcoma and neuroblastoma (if not MIBG avid).

Could be DOTATATE scans in neuroblastoma patients, when available, following discussion with Study Chair.

h Scans performed outside the four-week screening period as standard of care, are acceptable.

i Females of child-bearing age required a negative pregnancy test prior to entering study.

j Follow-up for participants remaining on study was every 6 weeks for the first 3 months, then every 3 months for up to 2 years from completion of therapy. Patients may need to be seen more frequently than these defined intervals based on their medical needs.

In instances where participants discontinued study drug before completion of therapy, they were encouraged to continue with study follow-up visits as long as such procedures did not pose a risk to the well-being of the patient.

Measurement of effect

Survival Measure

At each study visit (every 28 days) while on treatment, patient study status will be collected. If a patient terminates treatment early, the reason and date will be collected. This includes progressive disease, toxicity or adverse event, and death.

Follow-up for participants remaining on study will be every 6 weeks for the first 3 months, then every 3 months for up to 2 years from completion of therapy.

After treatment completion, patient death or lost to follow up will be collected at follow up visits.

Event Measure

Radiographic progressive disease will be captured in the overall response at each disease assessment as per section 9 of protocol. Clinical progression will be documented during study visits as described above.

Full details of the background to the trial and its design are presented in the protocol.

3. GENERAL STATISTICAL METHODOLOGY

3.1. SCOPE

The biological activity analysis was performed during the trial to determine dosing levels (real time acetylation data). This analysis and its results are not in the scope of this analysis. See section 4.3 of protocol for more information.

3.2. ANALYSIS SOFTWARE

All analyses will be performed using Stata Release 18 or later.

3.3. DATA VERIFICATION

All variables included in analysis will be assessed for validity. Range checks will be performed on all continuous variables. Categorical variables will be assessed for consistency with the protocol and relevant data dictionary. Any data verification queries will be raised with the study team.

3.4. DEFINITION OF BASELINE

Baseline will be defined period between consent date and date of enrolment.

Date of enrolment (day 0) will be the eligibility visit date in the database, *visdat*.

Baseline values used to define changes in measurements over time for each participant are defined as the closest to and including day 0 within the preceding 28 days. Where more than one measurement is available within this window the closest to enrolment will be used.

Patients were enrolled on the study once all eligibility requirements for the study were met. The National Coordinating Centre, in conjunction with the Study Chair, reviewed the submitted eligibility information and supporting source documentation.

Start of treatment is defined as (Week 1 Day 1 *visdat*) from the study status database.

3.5. ASSESSMENT OF RESPONSE

The revised Response Evaluation Criteria in Solid Tumours (RECIST), Version 1.1, will be used to evaluate tumour response for non-CNS solid tumours. The Response Assessment in NeuroOncology Working Group's updated response assessment criteria (RANO) will be used to evaluate tumour response for CNS solid tumours. The revised International Neuroblastoma Response Criteria will be used to evaluate tumour response for neuroblastoma. For further details of these definitions please refer to the protocol.

The study investigator's evaluation of overall response will be used in analysis.

3.6. ADVERSE EVENTS

Adverse events will be coded according to the Common Terminology Criteria for Adverse Events V4.0 (CTCAE V4.0).

3.7. YEAR, MONTH AND DURATION

The following conversion factors will be used to convert days to months or years: 1 month = 30.4375 days, 1 year = 365.25 days. Duration will be calculated as (end date – start date + 1).

4. DESCRIPTIVE STATISTICS

Analysis will be completed by disease strata;

MRT/ATRT (strata 1), osteosarcoma (strata 2), or neuroblastoma (strata 3).

4.1. RECRUITMENT AND FOLLOW-UP

A CONSORT flowchart of patient enrolment and follow up will be provided.

The number of patients and the proportions who were consented, screen failed, enrolled, completed treatment, and completed follow-up will be summarised by disease strata.

4.2. BASELINE CHARACTERISTICS

Patient and disease characteristics at baseline will be summarised by disease strata. Continuous variables will be reported with mean with range and categorical variables will be reported with frequencies and proportions. For neuroblastoma, results for the two individual patients will be reported. A listing of all characteristics for each patient will be provided.

This will include number with study indication (MRT/ATRT, osteosarcoma, neuroblastoma), disease event (newly diagnosed, relapsed, refractory, un-resectable lesion), number of relapse if applicable, disease status (stable disease, remission), central nervous system (CNS) disease, best response to prior treatment, prior surgery, prior chemotherapy, prior radiotherapy (RT) and location, RT total dose (Gy) if applicable, and other prior treatment.

Patient demographics summarised will include age, sex, ethnicity, indigenous status, and baseline performance score (Karnofsky \geq 16 years old, Lansky $<$ 16 years old).

4.3. PROTOCOL DEVIATIONS

Protocol deviations will be listed and summarised by disease strata.

4.4. COMPLIANCE

Mean (range) number of treatment courses completed (28 days per cycle) and time in follow up (weeks) will be summarised by disease strata. The number of patients who completed each course (full 28 days) will be listed for each disease strata, with reasons for early treatment termination listed.

Panobinostat dose (mg/m^2) days compliant, and total days of treatment will be summarised by mean and range by disease strata. A summary of dose received by treatment course will also be listed.

4.5. CONCOMITANT THERAPIES

All medications and significant non-drug therapies will be recorded throughout the study period. This includes medications commenced from 14 days before until 28 days after the study drug is administered. Medications include both prescribed and over the counter (OTC) medications including herbal and vitamin treatments.

A listing of concomitant medications will include medication name and reason sorted by disease strata.

5. ANALYSIS OF THE PRIMARY OUTCOME(S)

5.1. MAIN ANALYSIS

5.1.1. Event free survival

Primary Estimand

Population: All patients eligible and enrolled into trial with MRT/ATRT (strata 1), osteosarcoma (strata 2), or neuroblastoma (strata 3).

Treatment: Panobinostat

Outcome: Estimated 2-year Event free survival (EFS). EFS is calculated as the time from study enrolment to first documented disease progression, relapse or second malignancy, or death from any cause up to 2 years after study enrolment. The latest possible time of risk being 2 years after enrolment, or the last date known alive.

Summary measure: The probability of EFS (Kaplan-Meier) at with 95%CI will be estimated each stratum*. Kaplan- Meier curves will be plotted for EFS probability, enrolment date as start of risk period. Median EFS time will be calculated at 2 years post-enrolment.

**only calculated if stratum had adequate sample size (osteosarcoma and ATRT/MRT only).*

Subgroup Analysis:

Descriptive statistics (proportions) by subgroup for each disease strata.

Age at enrolment <36 months (3 years old) vs. ≥36 months

Radiation therapy (RT) vs. no RT

Disease status at trial entry (complete response vs stable disease)

Intercurrent Events

Potential intercurrent events:

Patient comes off study or treatment due to toxicity before an event is observed. Patient comes off study or treatment to receive another treatment.

Strategy for handling intercurrent event:

Treatment policy

EFS will be estimated for patients regardless of early treatment or trial termination. This approach assumes that data collected is reflective of those missing data (patients who withdrew from trial).

Sensitivity Analysis

Composite Strategy

Patients coming off study or protocol treatment due to an irreversible or unacceptable dose limiting toxicity or a Serious adverse event (SAE) before an event is observed, will be handled by the composite strategy. The removal from study/treatment date will be treated as an event.

Patients coming off study or protocol treatment to receive another treatment will also be handled by this strategy in the same analysis.

Primary Estimand Calculation

EFS will be estimated and visualised using the Stata sts list and graph commands.

```
stset tvar, fail(event) origin(time enrol_date) enter(time consent_date)
sts list, strata(disease type) risk table(6 12 24) sts graph, strata(disease type) risk
table(0 6 12 18 24) xlabel(0 6 12 18 24) tmax(24) Median EFS will be estimated
using Stata stsum command stsum, by(disease type)
```

Subgroup analysis

The proportion in each group and 95%CI will be estimated using Stata's *ci proportions* command.

Sensitivity analysis (as above with alternate event) *stset tvar, fail(event_comp) origin(time enrol_date) enter(time consent_date)*

Where time is in months and patients will be censored at their last known contact alive.

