5.1.2. Overall survival

Primary Estimand

Population: All patients eligible and enrolled into trial with MRT/ATRT (strata 1), osteosarcoma (strata 2), or neuroblastoma (strata 3).

Treatment: Panobinostat, dosing as per protocol.

Outcome: Estimated Overall Survival (OS). OS is calculated as the time from study enrolment to death from any cause.

Summary measure: The OS probability (Kaplan-Meier) and 95%CI will be estimated for each stratum* up to 2 years post-enrolment. Kaplan-Meier curves will be plotted for OS probability; enrolment date as start of risk period. The number of deaths and the median OS time will be reported up to 2 years post-enrolment.

**only calculated if stratum had adequate sample size (osteosarcoma and ATRT/MRT only).*

Subgroup Analysis:

As per section 5.1.1

Intercurrent Events

Potential intercurrent events:

Patient comes off study due to toxicity, or to start a new treatment.

Strategy for handling intercurrent event:

Patients coming off study due to a related toxicity or to start a new treatment will be handled with the treatment policy. OS will be analysed for all patients regardless of treatment received until last study visit.

Sensitivity Analysis

Composite Strategy

Patients coming off study due to toxicity or to start a new treatment before death could be observed will be handled by the composite strategy. The removal from study date will be treated as an event/death in sensitivity analysis.

Estimand Calculation

OS will be estimated and visualised using the Stata sts list and graph commands.

stset tvar, fail(death) origin(time enrol_date) enter(time consent_date) sts list,

strata(disease type)

sts graph, strata(disease type) tmax(24)

Median OS will be estimated using Stata stsum command *stsum,*

by(disease type)

Where time is in months and patients will be censored at their last known contact alive.

5.1.3 -Safety

Adverse events will be summarised by grade and type defined by CTCAE Version 4 from 1 week to 12 months after intervention commencement.

Relationship to study drug (definite, probable, possible) adverse events summarised in a table, with the worst AE grade reported by each participant.

A summary table of Dose Limiting Toxicities will include AE type, grade, and frequency.

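### Section 5.1.1 censors event-free survival at the last date known alive, which does not show freedom from progression; the effect can only keep or raise 2-year EFS, and may be zero

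*SAP*

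**What the plan says.** Section 5.1.1 defines EFS as time from enrolment to the first of progression, relapse, second malignancy or death, up to 2 years. It closes the risk period with "The latest possible time of risk being 2 years after enrolment, or the last date known alive", and its calculation part adds that "patients will be censored at their last known contact alive". Section 5.1.2 gives the OS rule in the same words: "Where time is in months and patients will be censored at their last known contact alive".

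The EFS sensitivity analysis is introduced as "Sensitivity analysis (as above with alternate event"; it changes the event and keeps the censoring date.

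Section 2.7 says how events come to be known:
- Imaging: "Radiographic progressive disease will be captured in the overall response at each disease assessment".
- Clinical progression: "Clinical progression will be documented during study visits as described above".
- Survival status: "After treatment completion, patient death or lost to follow up will be collected at follow up visits".
- Patients who stopped drug early: "they were encouraged to continue with study follow-up visits as long as such procedures did not pose a risk".

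Footnote e to the Section 2.7 schedule allows follow-up imaging every 3 months or as in routine care. Section 8 and Table 14 list the last contact, but not the date when event status was last established.

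**The concern.** For OS the rule is right: a patient known alive on a date has not died by that date. For EFS the same contact settles only one of the four event types. A patient last assessed at month 9 and merely known to be alive at month 12 would count as event-free for those three months, although nothing recorded supports it.

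Estimated 2-year EFS is a primary endpoint of a single-arm trial, so no control arm shares such an effect. Sections 2.2.3 and 7.1 also plan to compare EFS in ATRT patients with historical data. Any effect runs one way, and the tables as planned would not let a reader see whether it occurred.

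**Working it through.** **Inputs.** The SAP gives no EFS rate, event count or gap between last assessment and last contact, so it has no EFS figure to reproduce. Its sample-size figure of 14 (Section 2.6) concerns 4-month stability and does not bear on this point. Enrolment was 14 in ATRT/MRT and 9 in osteosarcoma (Section 2). All event times and gaps below are assumptions.

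**Step 1: direction.** The Kaplan-Meier estimate is S(24) = Π(1 − d_j/n_j) over event times up to month 24. With the events fixed, a later censoring date leaves each d_j unchanged and can only keep or enlarge each n_j. Every factor, and so S(24), is equal or higher. The rules give the same result if no event falls between a patient's two dates.

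**Step 2: worked example, n = 14.** Events at months 2, 2, 4, 4, 6, 8, 10 and 14; three patients event-free to month 24; three last assessed at month 9 and last known alive at month 12. After the month-8 event S = 8/14 under both rules.
- SAP rule (censor at 12): 8 at risk at month 10 and 4 at month 14. S(24) = 8/14 × 7/8 × 3/4 = 37.5% (95% CI 11.6 to 64.0, log-log Greenwood).
- Censor at 9: 5 at risk at month 10 and 4 at month 14. S(24) = 8/14 × 4/5 × 3/4 = 34.3% (9.4 to 61.6).
- With two such patients and four event-free to month 24: 40.0% v 38.1%. With one and five: 41.7% v 40.8%.

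**Step 3: average size by simulation, n = 14.** Assumptions: exponential progression with true 2-year EFS of 20%, 35% or 50%; death on average 9 months after progression; 20% or 35% of patients leave assessment at a time uniform on 2 to 18 months; vital status known for a further fixed gap. Both rules count the same events. No progression after the last assessment is learned; later deaths count up to last contact. Entries are percentage points, as ranges over scenarios.

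| Gap (months) | SAP rule minus truth | SAP rule minus last-assessment rule |
|---|---|---|
| 0 | −0.4 to +0.4 (noise) | 0 |
| 1.5 | +0.3 to +1.4 | +0.5 to +1.0 |
| 3 | +0.8 to +1.9 | +1.0 to +2.1 |
| 6 | +1.5 to +3.2 | +1.9 to +4.3 |
| 12 | +2.2 to +4.8 | +3.5 to +7.3 |

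Monte Carlo standard error is up to about 0.25 points; the standard deviation of one estimate is 12 to 16 points. For n = 9 and a 3-month gap, the SAP rule minus truth is +0.9 to +2.2.

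**Step 4: what if late progressions are partly learned?** If half of the progressions between last assessment and last contact are documented and counted:
- 3-month gap: SAP rule about +0.5 to +0.9; censoring at the last assessment about −0.4 to −1.1.
- 12-month gap: SAP rule about +1.1 to +2.3; censoring at the last assessment about −1.9 to −4.8.

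Here the stricter rule keeps patients at risk when their late contact reveals an event and drops them when it does not, so it errs downward.

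**The case against.** The strongest objection is that the two dates probably coincide for most patients. Section 2.7 collects death and loss to follow-up at follow-up visits, its schedule includes history, physical examination and performance status at those visits, and clinical progression is documented at study visits. Section 5.1.2 follows OS only to the last study visit, and the example entries for last contact in Table 14 are visit labels. The SAP describes no telephone, registry or survival-only follow-up. Patients who stop attending would usually lose both dates together. This stands, and it is why the size may be zero. It does not remove the point: the rule as written accepts any evidence of life, off-visit contact is not excluded, and early stoppers were only encouraged to attend.

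A reader might infer that the reported 2-year EFS will be inflated. The SAP does not support that, because it gives no gap. Nor do the 6- and 12-month rows of Step 3 describe this trial; scheduled follow-up is every 6 weeks for 3 months and then every 3 months.

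A reader might also infer that censoring at the last formal disease evaluation is plainly better. Step 4 shows it is not: counting every late event while discarding late contacts that recorded no event exchanges an upward bias for a downward one, which can be larger.

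**Conclusion.** Minor. Section 5.1.1 applies to EFS a censoring rule that fits only OS, and nothing elsewhere in the SAP corrects it. The direction is certain for the same set of events: 2-year EFS is equal or higher than when censored at the last date event status was known. That compares two rules; it does not say that the SAP estimate lies above the truth in this trial.

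The size is unknown from the SAP. It is zero if every last contact included an assessment for progression. Under the assumed 3-month gap it is about 0 to 2 points, small beside an interval as wide as 11.6% to 64.0% in the worked example. The SAP attaches no threshold or test to the EFS estimate, so no stated decision turns on it.

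**What to change.** In Section 5.1.1 replace both censoring phrases with wording such as:

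> Patients without an EFS event are censored at the last date, at most 2 years after enrolment, on which they were documented free of progression, relapse and second malignancy (imaging, clinical evaluation at a study visit, or any other contact at which disease status was recorded). A contact recording only that the patient is alive does not extend EFS time.

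Keep every documented progression, relapse, second malignancy and death up to 2 years as an event, so the event definition and the treatment-policy strategy stand. Report the present last-known-alive rule as a sensitivity analysis, add the last event-status date to Table 14, and leave OS as it is.

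The cost is two sentences, one row in Table 8 and one column in Table 14. Assessment dates are already needed for the clinical benefit rate (Section 6.1.1).

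The downside is slightly wider intervals and a possibly lower EFS. Some downward bias, growing with the gap, also remains if events after the last event-status date count while later alive-only contact does not. Letting any contact with recorded disease status extend EFS time limits this, and reporting both rules shows the range. If the two dates coincide, the new column will show it and the estimate will not change.

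### The composite EFS analysis in SAP 5.1.1 misses toxicity stops that are neither a DLT nor an SAE, and can then conflict with the composite OS analysis

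*SAP*

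**What the plan says.** SAP 5.1.1 lists two intercurrent events for EFS. The first is "Patient comes off study or treatment due to toxicity before an event is observed", with no condition on grade, seriousness or DLT status. The second is coming off to receive another treatment. The main analysis handles both by treatment policy.

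The composite sensitivity analysis in 5.1.1 covers patients who come off study or protocol treatment "due to an irreversible or unacceptable dose limiting toxicity or a Serious adverse event (SAE) before an event is observed". For them, "The removal from study/treatment date will be treated as an event". It adds: "Patients coming off study or protocol treatment to receive another treatment will also be handled by this strategy in the same analysis". Anyone not covered follows the ordinary EFS rule and is censored at last known contact alive if no event occurs.

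SAP 2.4 gives the reasons for which protocol therapy could end. Reason (b) is "Irreversible or unacceptable dose-limiting toxicity". Reason (c), listed separately, is "Other adverse event".

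For OS, SAP 5.1.2 words its composite rule as "Patients coming off study due to toxicity or to start a new treatment before death could be observed". The removal-from-study date then counts as an event or death. This rule has no DLT or SAE limit, but it covers only patients who leave the study. The composite rule for clinical benefit in 6.1.1 is broader: any early end of treatment counts as no benefit.

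**The concern.** The composite analysis is the check prespecified in 5.1.1 on how far toxicity stops affect the EFS result. It should count the event that the section names. As written, it counts a subset: DLT stops and SAE stops. A stop for an adverse event that is neither serious nor a DLT, which 2.4(c) allows for, falls outside it.

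Two things are at stake. The sensitivity result may understate the effect of toxicity stops. The composite EFS and composite OS analyses may also disagree about the same patient, with OS recording a death and EFS recording nothing, although death from any cause is itself an EFS event.

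**Working it through.** The plan states no figure on this point, so there is none to reproduce. The check sets the rules side by side and then bounds the size.

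**Inputs**
- Intercurrent events and composite EFS rule: SAP 5.1.1.
- Reasons for ending therapy: SAP 2.4(b) and 2.4(c), taken here as the two reasons under which a toxicity stop would be recorded.
- Composite OS rule: SAP 5.1.2.
- Stratum sizes: 14 enrolled in ATRT/MRT and 9 in osteosarcoma (SAP section 2, Study Expansion).

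**Step 1: classify the stops**

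| Why the patient comes off | Named intercurrent event in 5.1.1 | Composite EFS event at the stop | Composite OS event |
|---|---|---|---|
| DLT, 2.4(b) | Yes | Yes | Only if the patient leaves the study |
| Other adverse event, 2.4(c), serious | Yes | Yes | Only if the patient leaves the study |
| Other adverse event, 2.4(c), not serious; stays in follow-up | Yes | No | No |
| Other adverse event, 2.4(c), not serious; leaves the study | Yes | No; censored at last contact | Yes, at removal |
| To receive another treatment | Yes | Yes | Only if the patient leaves the study |

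The third and fourth rows are the gap. The fourth is also inconsistent between endpoints.

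**Step 2: can composite EFS exceed composite OS?** Because death is an EFS event, a patient's EFS time should never be longer than the OS time. The fourth row breaks this. Illustration: one such patient, and all others followed to 2 years without an event.
- ATRT/MRT: composite OS = 13/14 = 92.9%; composite EFS = 100%, because the patient is censored.
- Osteosarcoma: composite OS = 8/9 = 88.9%; composite EFS = 100%.

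This is a deliberately simple case. Progressions without death among the other patients would lower EFS and could hide the reversal in the curves. The patient-level conflict would remain.

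**Step 3: size per reclassified patient.** With complete 2-year follow-up, the Kaplan-Meier estimate equals a proportion. Reclassifying k patients who would otherwise be event-free at 2 years moves it by k/n.
- n = 14: 1/14 = 7.1 points, 2/14 = 14.3, 3/14 = 21.4.
- n = 9: 1/9 = 11.1 points, 2/9 = 22.2, 3/9 = 33.3.

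The values k = 1 to 3 are illustrative assumptions; the SAP does not give k.

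For a single patient who leaves the study, let r be the number at risk at that time, with all others fully followed, and let F be the fraction of the remaining r − 1 who are event-free to 2 years. Censoring gives (r/n)·F and an event gives ((r − 1)/n)·F. The difference is F/n, which is at most 1/n.

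With complete follow-up, a reclassified patient who progresses or dies before 2 years anyway changes the 2-year value by 0, although the curve and median may shift.

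**The case against.** The strongest reply is that the gap is narrow and confined to a sensitivity analysis. Much of that stands.
- A serious adverse event under 2.4(c) is already counted, and so is anyone who comes off to receive another treatment. Only non-serious, non-DLT stops outside that route are missed.
- A reader might infer that the missed patients stay event-free. They do not: they remain at risk for progression, relapse, second malignancy and death. What is missing is an event at the stop date.
- A reader might infer that every such patient is an OS composite failure and not an EFS one. The OS rule covers only removal from study, and SAP 2.7 encourages patients who stop the drug to stay in follow-up. The conflict arises only for those who also leave.
- A reader might infer that counting SAE stops without a relatedness condition is an error. The SAP does not say that the composite is limited to drug-related toxicity; the word related appears only in the OS treatment-policy text ("Patients coming off study due to a related toxicity or to start a new treatment will be handled with the treatment policy"). Counting any SAE that ends treatment avoids investigator attribution in an open-label single-arm trial and is defensible.
- The SAP does not define DLT, so the number in the gap could be small. Reasons for early termination are also listed (SAP 4.4, Table 5), so a reader of strata this small could see the stops left out.

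None of this removes the mismatch between the named event and the counted event, or the possible conflict with OS.

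**Conclusion.** The point holds in this limited form. The composite EFS rule in 5.1.1 does not cover the intercurrent event that the same section names. For a patient who leaves the study because of a non-serious, non-DLT adverse event, it also contradicts the composite OS rule in 5.1.2.

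The per-patient sizes in the working are ceilings. They assume complete follow-up of the other patients and that the reclassified patient has no other EFS event by 2 years. Censoring among the others would change the size of the step. How many patients are affected cannot be learned from the SAP.

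A reader might conclude that the primary result is biased. It is not: the main EFS and OS analyses use treatment policy and do not depend on this rule.

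**What to change.** In 5.1.1, define event_comp as any removal from study or treatment recorded under 2.4(b) or 2.4(c), plus removal to receive another treatment. Keep the removal date as the event date. Every toxicity removal counted in the OS composite is then also a composite EFS event.

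Keep three things as they are:
- The OS composite stays limited to removal from study. Applying the 2.4 reasons there would code stopping the drug as death in patients still alive and followed.
- The 6.1.1 composite keeps its rule that any early end of treatment is no benefit. The 2.4(b)/(c) definition would narrow it.
- No relatedness condition is added. If attribution is of interest, list stops for unrelated adverse events separately.

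The cost is one sentence in the SAP and a recoded flag. SAP 2.7 says that the reason and date of early termination are collected, including toxicity or adverse event, so no new data are needed. Only analysis coding changes. The downside is that composite EFS may be slightly lower.
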